1.3 Responsibilities

Medistat on behalf of the Sponsor (Dexcel Pharma Technologies, Ltd.) will conduct the statistical analysis.

1.4 Study Populations

Intent-to-treat (ITT) population

Intent-to-treat (ITT) population – all patients randomized for one of the treatment arms and treated with at least one chip of study treatment or underwent Subgingival debridement will be used for assessments related to efficacy and all safety evaluations.

Safety population

Safety population will be the same as ITT population and will be used for safety analyses.

Modified-Intention-to-Treat (mITT) population

All patients in the ITT population with no major protocol violations, used to confirm the assessments related to efficacy.

Per Protocol (PP) Population

All patients in the ITT population who completed the study according to the protocol and with no major protocol violations. Subjects who exceeded the time window allowed between visits as described in the protocol, will be excluded from the PP cohort:

The allowances between screening (visit 1) and baseline (visit 2) should not exceed 14±7 days

The allowances for visits 3, 4, 5, 6, 7 and 8 should not exceed 14±4 days

The allowances between visit 8 and visit 9 should not exceed 28±4 days

The allowances between visit 9 and visit 10 should not exceed 56±10 days

Additional PP population (PP2) will be defined, based on different time window allowances:

No limitation for the allowances between screening (visit 1) and baseline (visit 2)

The allowances for visits 3, 4, 5, 6, 7 and 8 should not exceed 14+7 days or 14-4 days

The allowance between visit 8 and 9 should not exceed 28±7 days

The allowance between visit 9 and 10 should not exceed 56+28 days or 56-14 days

1.5 Primary Efficacy Endpoint

At week 24, compared to baseline, the mean probing Pocket Depth (PD) reductions (absolute change) for the selected target implant/s will be used as the primary efficacy endpoint

1.6 Secondary Efficacy Endpoints

- PD measurement at week 24 compared to baseline in patients with baseline PD measurement of 6-8 mm inclusive.
- Bleeding on Probing (BOP) measurements at week 16 and 24 compared to baseline.
- PD measurement at week 16 compared to baseline.

Exploratory Analyses

The tertiary efficacy endpoints will include:

- PD, BOP and Relative Attachment Levels (RAL) measurements at week 24 compare to baseline in Responders patients. Responders patients are those patients which demonstrated at week 24 PD reduction of at least 1 mm from baseline PD of 5 mm or PD reduction of at least 2 mm from baseline PD of 6-8 mm inclusive.
- PD and BOP measurements at weeks 8 and 12 compared to baseline.
- Recession (R) and RAL measurements at weeks 8, 12, 16 and 24 compare to baseline.
- PD measurement at week 12 and 16 compared to week 24.
- PD, BOP, RAL and R measured at weeks 8, 12, 16 and 24 for all 4 sites (mesio-buccal, mid-buccal, disto-buccal and mid-lingual), surrounding the selected target implant/s, compared to baseline.

1.7 Safety Analysis

Safety will be evaluated based on AEs and oral inspections recorded at each visit.

1.8 Sample size

A total of 290 patients will be randomized, in order to analyse at least 123 patients for the Subgingival debridement + PerioChip® arm and at least 123 patients for the Subgingival debridement alone arm. Based on the current drop-out rate (after randomization) of 9%, the expected drop-out rate (after randomization) should be between 12%-15%

Based on previous phase IIa studies, the expected drop-out rate in this study will be between 20%-25%. Thus, it is estimated that approximately 375 patients will be screened in order to randomize up to 290 patients.

The sample size is determined based on relevant literature (Machtei et al. 2012) and previous phase IIa study (CLI/013P) that demonstrated substantial improvement (trend toward significant, $p = 0.07$) in PD reduction between PerioChip® and Placebo chip.

The rationale for sample size calculated is based on detecting a difference of 0.50 mm in PD reduction from baseline between PerioChip® and Placebo chip, with 5% statistical significance and 85% power.

A sample size of 123 in each group will have 85% power to detect a difference in means of -0.50 mm (the difference between a Group 1 mean, of -2.29 and a Group 2 mean, of -1.79) assuming that the common standard deviation is 1.30 using a two group t-test with a 0.05 two-sided significance level.

Statistical significance level for all statistical analysis was set to 5%.

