Page 20 - Study Design and Duration		The reason for preferring the above design over the Double-blind, Placebo-controlled design is that in previous clinical studies with PerioChip® it was evident that when used Placebo chips have worse clinical outcome compare to No-chip. Namely, periodontal pockets treated with Placebo chips showed less improvement in PD and attachment levels compare to No-chip treated pockets. It was also noted that at six months following the use of Placebo chips fewer incidences of patients were considered to have healthy pockets. The results of these studies suggest, that placing of the Placebo chip acting as a mechanical barrier preventing environmental/outsides improvement in the pockets (Perio Products-I; Perio products-II). Due to the above mentioned findings the use of Placebo treatment arm is less adequate. In this case excluding the Placebo arm from the study design ultimately prevents the establishment of Double-blind procedure.
Page 39 - Statistical methods		It is worth noting that although parameters used in the above calculation are derived from a placebo-controlled design, it is reasonable to assume this calculation is more conservative than if the parameter used were taken from previous studies where the study design included a treatment arm with no chip assigned, in Periodontitis patients. In other words, the sample size calculation is based on sound data derived from a study design which used the same indication (periimplantitis) and treatment regimen (frequent chip insertion) as appear in the current protocol

Dexcel Pharma Technologies Ltd

Page 58 - Reference List		
23. Perio Products.I. Clinical effects following subgingival administration of Chlorhexidine gluconate (2.5 mg) in a cross-linked gelatin matrix (PerioChip) in patients with periodontal disease (study 91-011). Clinical Study Report
 
24. Perio Products. II. Clinical effects following subgingival administration of Chlorhexidine gluconate (2.5 mg) in a cross-linked gelatin matrix (PerioChip) in patients with periodontal disease (study 91-013). Clinical Study Report

--------------------------	--	---

Summary of changes from version 3 dated 13 July2014 to version 4 dated 16 Nov. 2014

Page/Section	Original Text (version 3)	Amended Text (version 4)

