1.2 Design

This study is a multi-center, randomized, single-blind masking, parallel, two-arm clinical study.

The study duration will be 25-28 weeks (6 months) and will comprise a total of 10 visits: Screening and hygienic phase therapy (weeks -3 to -1), Baseline (week 0), week 2, week 4, week 6, week 8, week 10, week 12, week 16 and week 24 (follow up visit).

During the Baseline visit, eligible patients will be randomized to one of the following treatment regimens:

Treatment 1 – Subgingival debridement + Chlorhexidine Gluconate chip (PerioChip®) inserted every fortnight, for the first 12 weeks.

Treatment 2 – Subgingival debridement.

These treatments will be applied for at least 1 (one) and not more than 2 (two) implants in the oral cavity with clinical and radiographical signs of peri-implantitis. Peri-implantitis is defined as marginal bone loss of at least 3 mm from implant shoulder, and at least 2 mm distal and mesial supporting bone left from the apex to the coronal direction, in combination with bleeding and/or suppuration on probing and a peri-implant Probing Depth (PD) of 5-8 mm.

All pocket measurements (PD, BOP and R) and chip insertions will be made in the same order of procedures every time.

The same examiner will perform all the measurements during the study.

The person (physician/hygienist) placing the Chlorhexidine chips in the periodontal pockets or performing the Subgingival debridement, according to the randomization, will not be involved in target pockets measurements (i.e. the examiner and the physician/hygienist placing the chip or performing the Subgingival debridement will be two different persons).

In each patient meeting the entrance criteria, the deepest periodontal pocket of at least 1 (one) and no more than 2 (two) implant/s (if available) will be selected as a target pocket, and will be used for chip/s insertion or Subgingival Debridement and as the primary efficacy end-point.

The target pocket in the selected implant/s, will be treated at each visit with the same treatment arm, initiated at Baseline visit, as described below.

Implant/s which were not selected as target implant/s will be treated as per the investigators discretion as long as it does not affect the study inclusion/exclusion criteria (e.g. treatment with antibiotics or surgery next to a target implant included in the study).

Treatment 1: (PerioChip®)

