2. STATISTICAL METHODS

2.1 General

The change in efficacy parameters, PD, R and RAL during the 24 week treatment, will be modelled using a linear-mixed model (SAS® 9.3 Mixed Procedure) with treatment as fixed factors. Patient and pocket will be entered as random effects. The treatment-by-center interaction will be tested and if achieve statistical significance of $\leq 5\%$ will be added to the model as covariate. The analysis will be adjusted to the following covariates known to have influence on the efficacy parameters: age, gender, smoking status and baseline measurements. The adequacy of the Mixed Model will be checked and if needed a normalizing transformation will be performed. This model will be used for the reduction in PD, R and for improvement in RAL.

Contrasts with 95% Confidence Interval (C.I.) for the difference or ratio between the changes will be computed.

The Paired T-test or Signed rank test for two means (paired observations) (as is appropriate) will be applied for testing the statistical significance of the decrease in PD at each time point within each study group.

The two-sample T-test or Non-parametric Wilcoxon-Mann-Whitney Rank sum test for independent samples (as is appropriate) will be applied for testing the statistical significance of the difference in the percent PD decrease from baseline between the study groups.

Patients may have multiple pockets being treated. All treated pockets will be taken into account to create a by-pocket analysis in addition to the by-patient analysis.

Corresponding 95% C.I. for the difference between treatments not including zero for linear model, or 95% C.I. for the ratios between treatments not including unity for the log-linear regression will prove superior to treatment with PerioChip® versus Subgingival debridement.

Analysis for the number of pockets with at least 1 mm and at least 2 mm reduction in PD, and analysis for BOP for the target implant/s measured at each visit will be analyzed by a Chi-square test or Fisher's exact test as is appropriate.

Logistic regression will be applied for testing the above differences with adjustment to smoking status, Gingival Index (GI), medical center and other suspected confounders, if found. Odds Ratio and 95% Confidence Interval will be calculated using the Logistic model.

Similar mixed models for PD, R and RAL with time as a fixed repeated covariate will be used to reveal the changes of these parameters over time.

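### Does taking the 0.50 mm difference from a placebo-chip comparison undermine the sample size of a trial run against debridement alone?

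*SAP*

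**What the plan says.** SAP section 1.8 cites published literature and a phase IIa study of PerioChip against placebo chip (p = 0.07), and describes the calculation as "based on detecting a difference of 0.50 mm in PD reduction from baseline between PerioChip® and Placebo chip". It then states: "A sample size of 123 in each group will have 85% power to detect a difference in means of -0.50 mm", with group means of -2.29 and -1.79, a common SD of 1.30 and a two-sided 5% t-test. Up to 290 patients are randomized so that at least 123 per arm can be analysed.

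The control arm is given in SAP section 1.2 as "Treatment 2 – Subgingival debridement", with no chip of any kind. SAP section 2.1 sets the superiority criterion on that contrast: a 95% confidence interval that excludes no difference "will prove superior to treatment with PerioChip® versus Subgingival debridement".

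The protocol's summary of changes from version 2 to version 3 has two relevant entries. Under Study Design and Duration, the sponsor explains why there is no placebo arm: "periodontal pockets treated with Placebo chips showed less improvement in PD and attachment levels compare to No-chip treated pockets". Under Statistical methods, it acknowledges that the parameters come from a placebo-controlled design and says that "this calculation is more conservative than if the parameter used were taken from previous studies" with a no-chip arm in periodontitis patients. It adds that "the sample size calculation is based on sound data derived from a study design which used the same indication" and the same regimen of frequent chip insertion. The later entries for section 8.1 change only the numbers randomized, screened and dropping out. None withdraws this rationale.

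**The concern.** A power calculation should use the difference expected on the contrast that will be tested. Here the difference comes from another control, and the sponsor's reason for dropping that control suggests it flatters the active arm. If a placebo chip holds back healing, PerioChip will look better against a placebo chip than against no chip. The word conservative in the version 3 text then seems to point the wrong way, and no effect or SD from the no-chip studies is given to support it. SAP section 1.8 does not repeat the rationale, so someone reading only the SAP sees 85% power with no comment on the control.

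What is at stake is the chance of missing a real but smaller benefit, and how a non-significant result would be read. Type I error and the treatment estimate are not involved.

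**Working it through.** **Inputs.** From SAP section 1.8: difference δ = 2.29 − 1.79 = 0.50 mm, SD σ = 1.30 mm, two-sided α = 0.05, power 85%, 123 per arm, post-randomization drop-out 12–15%. Allocation is 1:1 (blocks of 6, three per arm, in the protocol's version 2 changes).

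**Reproducing the plan's figure.** By the normal approximation,

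n per arm = 2(1.960 + 1.036)²σ²/δ² = 2 × 8.98 × 1.69 / 0.25 ≈ 121.4, so 122.

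The exact noncentral t calculation gives 123. At 123 per arm the standard error is 1.30 × √(2/123) = 0.166 mm and the noncentrality is 0.50/0.166 = 3.02. Power is 85.5% by the normal approximation and 85.2% by the exact t-test. For drop-out, 246/(1 − 0.15) = 289.4, so 290. The arithmetic holds throughout.

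**How the control enters.** The formula uses only δ and σ, so the power statement is true for any control, provided the true difference is 0.50 mm with SD 1.30. What the control affects is how plausible 0.50 mm is:

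(PerioChip − no chip) = (PerioChip − placebo chip) − (no chip − placebo chip) = 0.50 − g.

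If g is positive for implants, the tested difference is below 0.50 mm. The documents give a direction for g in periodontal pockets only, and no size.

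**Sensitivity.** Exact t-test power (%), SD 1.30, two-sided 5%. Every difference other than 0.50 mm is an assumption, and so is the 20% of variance explained by covariates (SD becomes 1.30 × √0.80).

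| True difference (mm) | 123 per arm, unadjusted | 145 per arm, unadjusted | 145 per arm, 20% of variance explained |
|---|---|---|---|
| 0.60 | 95.0 | 97.5 | 99.2 |
| 0.55 | 91.1 | 94.9 | 98.0 |
| 0.50 | 85.2 | 90.4 | 95.4 |
| 0.45 | 77.2 | 83.6 | 90.7 |
| 0.40 | 67.1 | 74.3 | 83.1 |
| 0.35 | 55.7 | 62.7 | 72.4 |
| 0.30 | 43.8 | 49.9 | 59.1 |

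The 145 per arm is 290/2. It is an upper bound: the ITT set in SAP section 1.4 keeps treated patients who later drop out, but they contribute only partial information. The adjusted column is relevant because the principal model in SAP section 3.3.1 adjusts for baseline, age, gender, smoking and site. With 10% to 30% of variance explained, power at 0.40 mm and 145 per arm runs from 79% to 88%.

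**Reading a null result.** The 95% interval at 123 per arm has a half-width of about 1.97 × 0.166 = 0.33 mm. The reported interval therefore shows which differences a non-significant result excludes, whatever was assumed at the design stage.

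**The case for a change.** The strongest case for acting is that this is the SAP's only power statement, that the version 3 text makes a smaller difference more likely, and that a few words would fix it. Sharing the indication and regimen justifies the population and the schedule, but it does not justify the control. Under the least favourable reading, power is 44% at 0.30 mm. A true difference that small stays below 85% even with all 290 patients counted and 30% of variance explained (65%).

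Part of this stands. The source contrast and the tested contrast differ, the rationale carries no figures, and the SAP does not repeat it. The rest is inference. The placebo-chip evidence comes from periodontal pockets, and carrying it over to implants is the reader's step. The claim of conservatism compares the calculation with parameters from no-chip periodontitis studies. Those studies may have had a larger effect or a smaller SD, so the claim can be true alongside the placebo-chip finding. It cannot be checked or refuted here, because the protocol is available only as a summary of changes. At 0.40 mm the scenarios run from 67% to 88%, so the table does not settle whether power falls short.

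**Conclusion.** No change follows. The plan's figure is right as the conditional statement it is: 85.2% power at 123 per arm if the difference is 0.50 mm and the SD 1.30. The placebo-chip source is named in SAP section 1.8 and defended in the protocol's version 3 changes. Choosing parameters from the same disease and dosing regimen over parameters from the right control in a different disease is a fair trade-off when neither source matches fully.

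The loss of power could be large if the true difference were well below 0.50 mm (67.1% at 0.40 mm, unadjusted, 123 per arm). That depends on an assumed difference, an assumed carry-over from periodontal data, and no credit for covariate adjustment or for more than 123 analysed per arm. The documents supply no value that would support a different sample size. A caveat or sensitivity table in SAP section 1.8 would record the uncertainty, but the confidence interval already tells a reader what a non-significant result rules out.

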1.9 Interim Analyses

No interim analyses are planned.

2. STATISTICAL METHODS

2.1 General

The change in efficacy parameters, PD, R and RAL during the 24 week treatment, will be modelled using a linear-mixed model (SAS® 9.3 Mixed Procedure) with treatment as fixed factors. Patient and pocket will be entered as random effects. The treatment-by-center interaction will be tested and if achieve statistical significance of $\leq 5\%$ will be added to the model as covariate. The analysis will be adjusted to the following covariates known to have influence on the efficacy parameters: age, gender, smoking status and baseline measurements. The adequacy of the Mixed Model will be checked and if needed a normalizing transformation will be performed. This model will be used for the reduction in PD, R and for improvement in RAL.

Contrasts with 95% Confidence Interval (C.I.) for the difference or ratio between the changes will be computed.

The Paired T-test or Signed rank test for two means (paired observations) (as is appropriate) will be applied for testing the statistical significance of the decrease in PD at each time point within each study group.

The two-sample T-test or Non-parametric Wilcoxon-Mann-Whitney Rank sum test for independent samples (as is appropriate) will be applied for testing the statistical significance of the difference in the percent PD decrease from baseline between the study groups.

Patients may have multiple pockets being treated. All treated pockets will be taken into account to create a by-pocket analysis in addition to the by-patient analysis.

Corresponding 95% C.I. for the difference between treatments not including zero for linear model, or 95% C.I. for the ratios between treatments not including unity for the log-linear regression will prove superior to treatment with PerioChip® versus Subgingival debridement.

Analysis for the number of pockets with at least 1 mm and at least 2 mm reduction in PD, and analysis for BOP for the target implant/s measured at each visit will be analyzed by a Chi-square test or Fisher's exact test as is appropriate.

Logistic regression will be applied for testing the above differences with adjustment to smoking status, Gingival Index (GI), medical center and other suspected confounders, if found. Odds Ratio and 95% Confidence Interval will be calculated using the Logistic model.

Similar mixed models for PD, R and RAL with time as a fixed repeated covariate will be used to reveal the changes of these parameters over time.

All treatment comparison will be two-sided at the 0.05 level of significance.

The data will be analyzed using the SAS® version 9.3 (SAS Institute, Cary North Carolina) or higher version.

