3.3.1 Principal Analysis

The change in efficacy parameters, PD, during the 24 week treatment, will be modelled using a linear-mixed model (SAS® 9.3 Mixed Procedure) with treatment as fixed factors. Patient and pocket will be entered as random effects. Interactions between treatment and the covariates will be tested and if achieve statistical significance of $\leq 5\%$ will be added to the model as covariate. The analysis will be adjusted to the following covariates known to have influence on the efficacy parameters: age, gender, smoking status, site and baseline measurements. The adequacy of the Mixed Model will be checked and if needed a normalizing transformation will be performed.

Contrasts with 95% C.I. for the difference between the changes by week will be computed.

The Paired T-test or Signed rank test for two means (paired observations) (as is appropriate) will be applied for testing the statistical significance of the decrease in PD at each time point within each study group.

The two-sample T-test or Non-parametric Median test for independent samples (as is appropriate) will be applied for testing the statistical significance of the difference in the PD decrease from baseline between the study groups.

Categorical analysis will be applied for PD change at week 24, using median value calculated overall subjects. Logistic regression will be applied for categorical PD change with adjustment to baseline measure, age, gender, site and smoking status. Interactions between treatment and the covariates will be tested and if found statistically significant, will be added to the model.

Analysis of Variance (ANOVA) will be applied for analysing PD change at week 24, with adjustment to baseline measure, age, gender, site and smoking status. Interactions between treatment and the covariates will be tested and if found statistically significant, will be added to the model.

Missing data will be handled for imputation the primary endpoint data using the MMRM model (Mixed-effect Model for Repeated Measures), which is based on MAR (missing at random) assumption.

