3.4 Secondary Efficacy Endpoints

The secondary efficacy endpoints are:

- PD measurement at week 24 compared to baseline in patients with baseline PD measurement of 6-8 mm inclusive.
- Bleeding on Probing (BOP) measurements at week 16 and 24 compared to baseline.
- PD measurement at week 16 compared to baseline.

The analysis of the secondary endpoints will be based on ITT, mITT, PP and PP2 populations.

Multiplicity

The secondary efficacy endpoints will be analysed according to pre-defined order:

1. PD changes at 24 weeks from baseline in patients with baseline PD of 6-8 mm inclusive.
2. BOP changes at 24 weeks from baseline
3. BOP changes at 16 weeks from baseline
4. PD changes at 16 weeks from baseline

The following stages will be applied:

1. The 1st secondary endpoint in the ordered list will be tested at 5% significance level. If it achieves statistical significance then the 2nd secondary endpoint will be analysed (stage 2). Otherwise the other secondary endpoints in the list will not formally be tested.
2. The 2nd secondary endpoint in the ordered list will be tested at 5% significance level. If it achieves statistical significance then the 3rd secondary endpoint will be analysed (stage 3). Otherwise the other secondary endpoints in the list will not formally be tested.
3. The process will continue for all the secondary endpoints according to the list until a secondary endpoint is not significant or until all secondary endpoints have been found significant.

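### The SAP's superiority rule (2.1) is not tied to week-24 PD, one analysis set, one unit of analysis or the side favouring PerioChip

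*SAP*

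**What the plan says.** **The rule.** SAP 2.1 (General) says that a "Corresponding 95% C.I. for the difference between treatments not including zero for linear model", or a ratio interval "not including unity for the log-linear regression will prove superior to treatment with PerioChip® versus Subgingival debridement".

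**Where it sits.** The same section describes a linear mixed model and adds: "This model will be used for the reduction in PD, R and for improvement in RAL". Its contrasts are described as "Contrasts with 95% Confidence Interval (C.I.) for the difference or ratio between the changes will be computed", with no week given. SAP 3.3.1 is specific to PD and does refer to weeks: "Contrasts with 95% C.I. for the difference between the changes by week will be computed". SAP 3.5 repeats that instruction for PD, R and RAL.

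**The roles of the endpoints.**
- SAP 1.5 and 3.3 make PD reduction at week 24 primary.
- SAP 1.6 lists PD at weeks 8 and 12 as exploratory. It does the same for "Recession (R) and RAL measurements at weeks 8, 12, 16 and 24 compare to baseline".
- SAP 3.4 puts four secondary endpoints in a fixed order, with PD at week 16 last. If a step fails, "Otherwise the other secondary endpoints in the list will not formally be tested".

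**Populations and units.** SAP 3.3 has the primary endpoint analysed in ITT, mITT, PP and PP2, each by pocket and by patient. SAP 1.4 gives ITT the efficacy assessments and mITT a confirming role.

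**Sidedness.** SAP 2.1 makes all treatment comparisons two-sided at 0.05. The only direction given is the planning assumption in SAP 1.8, mean changes of -2.29 and -1.79 mm.

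**The concern.** A decision rule should identify one interval. This one identifies a family. The word that opens it refers back to intervals from a model used for three parameters, and the more specific sections compute such intervals at several visits. SAP 1.5 and 3.3 define the primary endpoint but do not say that superiority is judged on it alone. SAP 3.4 orders the secondary endpoints, but does not make the sequence depend on the primary result and does not say that a step passes only when the difference favours PerioChip.

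What is at stake is a report in which week-24 PD is not significant, an earlier PD contrast is, and superiority is claimed with a reference to SAP 2.1. A reader could object by pointing to the endpoint labels, but the rule itself would not settle the argument. The same applies to a result seen in one population or one unit of analysis and not in another.

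**Working it through.** **1. The plan's own figure.** Inputs from SAP 1.8: difference 0.50 mm, SD 1.30, two-sided 0.05, power 85%.

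Normal approximation: n = 2 × (1.960 + 1.036)² × 1.30² / 0.50² = 2 × 8.98 × 6.76 ≈ 121.4, so 122 per arm. With the noncentral t distribution the smallest n is 123, with power 85.2%. The stated 123 per arm reproduces. It is the sample size for one comparison.

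**2. What one comparison gives.** At 123 per arm the standard error is 1.30 × √(2/123) = 0.166 mm. With no treatment effect, one 95% interval excludes zero 5% of the time: 2.5% on PerioChip's side and 2.5% on the other.

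**3. How many intervals fit the wording.**
- PD at weeks 8, 12, 16 and 24: 4 contrasts.
- PD, R and RAL at those weeks: 3 × 4 = 12 contrasts.
- Week-24 PD alone: 4 populations × 2 units = 8 analyses.

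**4. If any of the four PD weeks counted.** For independent contrasts the chance of at least one exclusion is 1 - 0.95⁴ = 18.5%; on PerioChip's side only, 1 - 0.975⁴ = 9.6%. Repeated measurements are correlated, but the documents give no correlation, so a range was simulated: 400,000 null draws of four z statistics with equal pairwise correlation ρ, counting any |z| > 1.96.

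| Assumed ρ | At least one interval excludes zero | At least one on PerioChip's side |
|---|---|---|
| 0 (formula) | 18.5% | 9.6% |
| 0.3 | 17.3% | 8.7% |
| 0.5 | 15.6% | 7.8% |
| 0.7 | 13.1% | 6.6% |
| 0.9 | 9.3% | 4.7% |

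The second column compares with 5%, the third with 2.5%. The inflation remains if only favourable results are counted.

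**5. All 12 contrasts, for illustration only.** The same method gives 17.6% to 43.5% two-sided, and 8.8% to 23.9% on the favourable side, over assumed between-week correlations of 0.3 to 0.9 and between-parameter correlations of 0 to 0.8. These figures require the exploratory labels in SAP 1.6 and 3.5 to be ignored.

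**6. After the fix.** With one contrast, one population, one unit and one side, the chance of a false superiority finding is 2.5%. The 123 per arm and 85.2% power stand.

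**The case against.** The strongest reply is that the SAP already says which result matters. Week-24 PD is primary in 1.1, 1.5 and 3.3; 3.3.1 is headed as the principal analysis and deals with PD only; weeks 8 and 12 and all R and RAL contrasts are labelled exploratory; and 3.4 withholds formal testing of week-16 PD if an earlier step fails. On the usual principle that specific sections govern general ones, the sentence in 2.1 means week-24 PD. The by-week instruction is in 3.3.1 and 3.5, not in 2.1, and neither section repeats the superiority sentence. No passage says that a by-week contrast proves superiority.

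Much of this stands. It shows what the authors probably meant, and it rules out reading 2.1 as a deliberate licence to bypass the sequence. It does not supply the missing link: no section restricts the rule to the primary endpoint, and none chooses between by-pocket and by-patient.

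A reader might go further and infer that an adverse result would count as proof. Literally, the rule names no side of zero. But the word superior implies benefit, and a two-sided test followed by a directional conclusion is ordinary practice. Nor do the documents show that harm is likely. The protocol's change summary reports that "periodontal pockets treated with Placebo chips showed less improvement in PD and attachment levels compare to No-chip treated pockets", but that concerns drug-free chips, not PerioChip. SAP 1.8 cites a phase IIa trend for PerioChip over the placebo chip (p = 0.07). One can calculate that if PerioChip were truly 0.25 mm worse, the interval would lie on the wrong side about 32% of the time, but that 0.25 mm is in no document.

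**Conclusion.** The point holds as a gap in the wording of the decision rule. As written, SAP 2.1 does not confine a superiority conclusion to week-24 PD, one analysis set, one unit of analysis or the favourable side, although other sections imply most of these. If any of the four PD weeks were allowed to satisfy it, the two-sided chance of at least one exclusion under no effect would be roughly 9% to 17% instead of 5%, for an assumed between-visit correlation of 0.9 to 0.3.

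The documents do not support the stronger inference that the trial's error rate is that high or higher, because the endpoint labels, if followed, prevent it.

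One limit applies. That 2.1 is the only superiority rule is true of the available text. The protocol document is a summary of changes, so its full statistical section could not be checked, and the SAP text was not quite complete.

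Severity: should be fixed; not an obstacle to the trial's design.

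**What to change.** Replace the sentence in SAP 2.1 with:

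> Superiority of PerioChip is concluded only if, in the ITT population and one named unit of analysis (by-patient or by-pocket, stated here), the two-sided 95% CI for the between-arm difference in PD change from baseline at week 24 lies wholly on the side of greater reduction with PerioChip or, if a log transformation is used, the ratio CI lies wholly on that side of unity. The sequence in 3.4 is opened only if this is met, and each step passes only in favour of PerioChip. All other populations, units, weeks and R or RAL contrasts are supportive or descriptive.

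The ratio clause is kept because 2.1 and 3.3.1 allow a normalizing transformation. The unit should be stated for the steps in 3.4 as well: the table list in Appendix I has by-patient tables for the primary endpoint but only by-pocket tables for the secondary ones.

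The cost is SAP wording. The sponsor gives up claiming superiority from other contrasts, and secondary claims become conditional on the primary result. Sample size and power do not change.
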